5.1 Study Assessments

5.1.1 Informed Consent

Subjects will be given a verbal explanation of the study and the procedures involved and will have all questions addressed. The subject must sign and date a consent form that has been approved by the appropriate Institutional Review Board (IRB)/Independent Ethics Committee (IEC) before the screening procedures are initiated. All subjects will be given a copy of the signed and dated informed consent form.

5.1.2 Subject Eligibility

All subjects will be assessed for eligibility against the inclusion and exclusion criteria described in Sections 4.3 and 4.4 and background clinical information collected.

5.1.3 Medical History

Medical history will be collected for the time period between a subject's completion of the final follow-up visit in study LAL-CL01 and the subject's first screening assessment in the extension study.

5.1.4 Demographic Information

Demographic information will not be recorded during screening for the extension study, as this information was previously recorded during screening for study LAL-CL01.

5.1.5 Physical Examination

A general physical examination will be performed by the Investigator or qualified designee. A complete physical examination will be conducted at the timepoints specified in Appendix A. The examination will include an assessment of the subject's general appearance, skin, head, eyes, ears, nose, and throat (HEENT), heart, lungs, abdomen, extremities/joints, and neurological status. Whenever possible, the same person should perform the physical examination at each study visit. Abnormal findings will be recorded in the eCRF. Height will be measured at the screening examination, and weight will be measured at all physical examinations.

The physical examinations will also include the following:

- Liver size: A clinical assessment of liver size (palpable/non palpable and centimeters below costal margin), regularity (smooth/nodular) and sensitivity (tender/non tender) will be made.
- **Spleen size:** A clinical assessment of spleen size (palpable/non palpable and centimeters below costal margin), regularity (smooth/nodular) and sensitivity (tender/ non-tender) will be made.
- **Lymphadenopathy:** An assessment of the size, location, and character of any palpable lymph nodes will be made. Areas to be examined include cephalic (occipital, preauricular, postauricular, submental, submandibular), cervical, clavicular, axillary, and inguinal. Any enlarged nodes will be characterized as tender or non-tender.
- Arterial disease: Right and left Posterior Tibialis and Dorsalis Pedis pulses will be assessed clinically.

5.1.6 Health-Related Quality of Life (HRQOL) Outcomes

Subjects will be instructed to complete the following HRQOL questionnaires at the timepoints specified in Appendix A:

- SF-36[®] (refer to Appendix B for details)
- FACIT-Fatigue (refer to Appendix C for details)
- CLDQ (refer to Appendix D for details)

Questionnaires should be administered in the same sequence at each study visit, and prior to any other study procedures being conducted at that visit. Detailed instructions on administration of HRQOL questionnaires are provided in the Study Operations Manual (SOM). The SF-36 was developed during the Medical Outcomes Study to measure generic physical and mental health concepts relevant across age, disease, and treatment groups. A total of 21 items within the 4 subscales of physical functioning, role-physical (i.e., role limitations due to physical problems), bodily pain, and general health compose the Physical Health summary measure and a total of 14 items within the 4 subscales of vitality, social functioning, role-emotional (i.e., role limitations due to emotional problems), and mental health compose the Mental Health summary measure

Page 29 of 76

(one item, self-reported health transition, is not included in a summary measure). In addition to the scores for each subscale, higher-order summary scores, the Physical Component Summary (PCS) and Mental Component Summary (MCS), are derived using standard scoring algorithms based on the correlation of each of the 8 subscales with physical and mental health, respectively. The SF-36 can be administered in approximately 5-10 minutes. In this study, the SF-36 version 2 will be self-administered. A sample questionnaire is provided in Appendix B.

The 13-item FACIT-Fatigue scale was developed to measure levels of fatigue in people living with a chronic disease. In this study, the FACIT-Fatigue scale version 4 will be self-administered. A sample questionnaire is provided in Appendix C.

The CLDQ is a disease-specific instrument designed to assess health-related quality of life in subjects with chronic liver disease. In this study, the CLDQ will be self-administered. A sample questionnaire is provided in Appendix D.

5.1.7 Abdominal MRI/MRS

Abdominal MRI and ¹H-MRS will be performed at the timepoints specified in Appendix A to quantify the organ volume and fat content of both the liver and spleen. Whenever feasible, additional abdominal imaging scans will be obtained at the same timepoints using ¹³C-MRS to permit an exploratory analysis of the liver cholesteryl ester signature. All MR imaging and spectroscopy will be performed by an MR technician or other qualified individual.

Detailed instructions on image acquisition and analysis will be provided in the Imaging Manual.

5.1.8 Vital Signs

Vital signs, including pulse rate, respiratory rate, systolic and diastolic blood pressure, and body temperature, will be measured at the timepoints specified in Appendix A. On dosing days, vital signs will be recorded pre-infusion and every 30 (±10) minutes during infusion and from 0 to 4 hours after completion of the infusion. Additional readings may be taken at the discretion of the Investigator in the event of an IAR. For each subject, the duration of post-infusion vital sign monitoring may be shortened to 2 hours after 6 months of treatment with no occurrence of IARs, and to 1 hour after 12 months of treatment with no occurrence of IARs, contingent upon approval by the Sponsor.

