7.1.3 Infusion Associated Reactions

Infusion-associated reactions will be considered AEs of special interest. Any AE that occurs during the infusion or within 4 hours after the infusion and is assessed by the Investigator as at least possibly related to IMP will be designated as an IAR. In addition, if, at any time during the study, the Investigator observes symptoms that he/she considers to be consistent with an IAR or a hypersensitivity reaction related to the administration of IMP, the symptoms will be recorded as an AE(s) and designated as an IAR(s).

As with any ERT, medications and equipment for the treatment of hypersensitivity reactions must be available for immediate use in case of unexpected severe hypersensitivity reactions. These supplies include, but are not restricted to, oxygen, acetaminophen, antihistamines (e.g. diphenhydramine, parenteral and oral [PO]), corticosteroids, epinephrine, and cardiopulmonary resuscitation devices.

General guidelines for classifying the severity of a reaction are provided below, and examples of mild, moderate, and severe IARs are provided in Appendix F.

For similar biological products, most acute IARs occur within 2 hours of the infusion. Signs of a possible acute IAR may include:

• Hyperemia, flushing, fever and/or chills, nausea, pruritus, urticaria, gastro-intestinal symptoms (vomiting, diarrhea, abdominal cramping), cardiopulmonary reactions, including chest pain, dyspnea, wheezing, stridor, hypotension or hypertension.

Page 40 of 76

If any of the above signs and symptoms are observed during the infusion and the subject does not show any respiratory symptoms and remains hemodynamically stable:

- a) The infusion rate must be slowed (reduced to half the rate being given at the onset of the event, e.g. from 125 mL/hr to 62.5 mL/hr) and the infusion time extended. Once the event has resolved, the infusion should continue for a minimum of 30 minutes at the reduced rate before the rate is increased to 75% of the original rate on the infusion schedule.
- b) In accordance with institutional standard of care for the subject's age, treatment with an antihistamine should be considered.

In subjects who experience severe infusion reactions with clinically significant cardiovascular effects (hypotension defined as a decline approaching 20-30% of their pre-infusion value), respiratory effects (significant shortness of breath, stridor, laryngeal edema or swelling of tongue), or other effects:

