8.7 Safety Analysis

Safety will be analyzed in Safety Analysis Set. As appropriate, the effect of dosing regimen and/or treatment duration on safety endpoints will also be explored.

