8.7.1 Adverse Events

All AEs, SAEs, and IARs will be coded using the Medical Dictionary for Regulatory Activities (MedDRA) and presented in by-subject listings that will include dosing regimen prior to the event, time of onset, severity, causality, actions taken regarding treatment, and outcome. The number and percent of subjects experiencing any AE, any SAE, any IAR, any related AE, any related SAE, and discontinuations due to an AE will be tabulated.

Treatment-emergent AEs, SAEs, and IARs will be tabulated (frequencies and percentages) by Preferred Term (PT) within System Organ Class (SOC), for all events and for events by severity and causality. If a subject experiences more than one occurrence of the same AE, and these differ in severity and/or causality, the AE will be tabulated according to the greatest severity and nearest relationship to IMP. As appropriate, additional listings and summary statistics will be generated to evaluate IAR frequency and severity over time. A listing of subjects who withdraw from the study due to AEs will be presented, and the incidence of AEs leading to study discontinuation will be summarized.

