⁷ Vital signs will be measured pre-dose, every 30 (±10) minutes during the infusion, and from 0 to 4 hours post-infusion. Post-infusion observation period may be shortened to 2 hours after 6 months of treatment with no occurrence of IARs, and to 1 hour after 12 months of treatment with no occurrence of IARs, contingent upon approval by the Sponsor.

⁸ This visit should occur 7 days after the Week 24 infusion. If scheduling does not permit, the visit may instead be scheduled 7 days after either the Week 26 or Week 28 infusion.

Page 58 of 76

Repeating 52-Week Schedule of Assessments: Week 54 through Study Completion*^{*}

	Wk	Wk	Wk	Wk	Wk	Wk	Wk	Wk	Wk	Wk	Wk	Wk	Wk	Wk	Wk	Wk	Wk	Wk	Wk	Wk						
Year 2	54	56	58	60	62	64	66	68	70	72	74	76	78	80	82	84	86	88	90	92	94	96	98	100	102	104
Year 3	106	108	110	112	114	116	118	120	122	124	126	128	130	132	134	136	138	140	142	144	146	148	150	152	154	156
Year 4	158	160	162	164	166	168	170	172	174	176	178	180	182	184	186	188	190	192	194	196	198	200	202	204	206	208/
Year 5	210	212	214	216	218	220	222	224	226	228	230	232	234	236	238	240	242	244	246	248	250	252	254	256	258	260
																										End of
																										Study ^{°,9}
Assessments	±7	±7	±7	±7	±7	±7	±7	±7	±7	±7	±7	±7	±7	±7	±7	±7	±7	±7	±7	±7	±7	±7	±7	±7	±7	±7
	days	days	days	days	days	days	days	days	days	days	days	days	days	days	days	days	days	days	days	days						
Health-Related Quality													x													х
of Life ¹													~													~
12-lead ECG													XP													X ^P
Physical Examination ²							XP						XP						XP							X ^P
Urine Pregnancy Test		XP		XP		XP		XP		XP		XP		XP		XP		XP		XP		XP		XP		X ^P
Clinical Laboratory							vP						vP						vP							v ^p
Tests ³							^						^						^							^
Liver and Lipid Panels							X ^P						XP						XP							X ^P
Coagulation Tests ³							XP						XP						XP							X ^P
Anti sebelipase alfa							٧ ^P						٧ ^P						٧ ^P							×٩
Antibody							^						^						^							Λ
Serum and Urine																										
Exploratory Biomarker							X ^P						X ^P						X ^P							XP
Collection																										
PK Profile ⁴																										X ⁷
Abdominal MRI/MRS ⁵																										Х
Liver Biopsy ⁶														Х ⁶												
Vital Signs ⁷	Х	Х	Х	Х	Х	Х	Х	Х	Х	Х	Х	Х	Х	Х	Х	Х	Х	Х	Х	Х	Х	Х	Х	Х	Х	X ⁸
Sebelipase alfa Dosing	Х	Х	Х	Х	Х	Х	Х	Х	Х	Х	Х	Х	Х	Х	Х	Х	Х	Х	Х	Х	Х	Х	Х	Х	Х	X ⁸
Adverse Events													Cor	tinuo	us											
Concomitant													Cor	tinuo	us											

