11.4 Vital Signs

Observed values and change from pre-dose will be presented for the following vital sign parameters, where applicable:

- Body temperature.
- Pulse rate.
- Blood pressure.

• Respiratory rate.

A listing of the vital signs measurements will be also provided.

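### Post-infusion observation may shorten from 4 h to 2 h and then 1 h while the IAR window stays at 4 h, so summaries of IAR frequency over time can be biased downward in later periods

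*Protocol*

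**What the plan says.** **Observation.** Protocol 5.1.8 sets vital signs on dosing days before the infusion and "every 30 (±10) minutes during infusion and from 0 to 4 hours after completion of the infusion". It then allows, subject by subject, that "the duration of post-infusion vital sign monitoring may be shortened to 2 hours after 6 months of treatment with no occurrence of IARs". The same sentence goes on to a second step: "and to 1 hour after 12 months of treatment with no occurrence of IARs, contingent upon approval by the Sponsor". The Appendix A footnotes describe the first step more broadly: "Post-infusion observation period may be shortened to 2 hours after 6 months of treatment with no occurrence of IARs".

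**Definition.** Protocol 7.1.3 designates as an IAR "Any AE that occurs during the infusion or within 4 hours after the infusion" that the Investigator judges at least possibly related. SAP 11.2.2 uses the same 4-hour limit. Neither window changes with time on study. Protocol 7.1.3 also lets the Investigator designate an IAR at any time.

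**Analysis.** IAR incidence is among the primary safety endpoints. Protocol 8.7.1 says "additional listings and summary statistics will be generated to evaluate IAR frequency and severity over time", and Protocol 8.7 says "the effect of dosing regimen and/or treatment duration on safety endpoints will also be explored". Both statements apply only where judged appropriate. SAP 11.2.2 specifies whole-study IAR counts and no by-period summary, but SAP Section 14 does not list the over-time evaluation as dropped. For vital signs, SAP 11.4 says "Observed values and change from pre-dose will be presented for the following vital sign parameters, where applicable". Neither document mentions the changing length of observation in connection with any analysis.

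**The concern.** The effort to detect IARs can fall along the same axis, time on drug, on which IARs are to be evaluated. Several signs listed in Protocol 7.1.3, such as fever, hypotension and hypertension, may be found only because someone measures them. A subject who has left after 1 hour may not notice them, and later questioning cannot recover a reading that was not taken.

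If the true IAR rate were constant, fewer hours of observation could still produce a lower recorded rate in later years. With up to 9 subjects and no formal tests, the long-term safety picture rests on descriptive patterns, and a few unrecorded events could change them.

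The vital-sign summaries are affected too. Late post-infusion readings in later years come from subjects whose observation was not shortened, or was shortened less, and from extra readings taken because of an IAR.

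**Working it through.** The documents state no IAR rate or capture rate, so there is no plan figure to reproduce. The check has four steps.

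**1. How much of the window is observed.** Inputs: 4, 2 and 1 h after infusion (Protocol 5.1.8); infusion of about 120 minutes (SAP 8.1.2).

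| Post-infusion observation | Readings at 30-min spacing | Share of 4 h post-infusion, w/4 | Share of full IAR window, (2+w)/(2+4) |
|---|---|---|---|
| 4 h | 8 | 100% | 100% |
| 2 h | 4 | 50% | 67% |
| 1 h | 2 | 25% | 50% |

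**2. How many infusions could be affected.** Appendix A schedules infusions at Weeks 1–4 and then every 2 weeks from Week 6 to Week 260: 4 + 128 = 132, counting Week 260 as a dosing visit. They split as 15 to Week 26, 13 from Week 28 to Week 52, and 104 after Week 52. So up to 104/132 = 79% could fall under the 1-hour rule. This is an upper bound: it needs an IAR-free subject on every-other-week dosing, with each step approved at the earliest date.

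**3. Effect on the recorded rate.** With a constant true rate, in a later period:

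recorded/true = 1 − (1−p) × q × (1−s)

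- p: share of IARs arising in subjects still observed for 4 h
- q: among the other IARs, the share starting after shortened observation ends but within 4 h
- s: share of those late IARs captured by later AE questioning (Protocol 7.3)

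None of the three is in the documents. The values below are assumptions.

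| q | p=0, s=0 | p=0, s=0.5 | p=0.5, s=0 | p=0.5, s=0.5 | any p, s=1 |
|---|---|---|---|---|---|
| 5% | 0.95 | 0.975 | 0.975 | 0.988 | 1.00 |
| 10% | 0.90 | 0.95 | 0.95 | 0.975 | 1.00 |
| 20% | 0.80 | 0.90 | 0.90 | 0.95 | 1.00 |
| 40% | 0.60 | 0.80 | 0.80 | 0.90 | 1.00 |

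For example, q = 20%, p = 0.5 and s = 0.5 give 1 − 0.5 × 0.20 × 0.5 = 0.95. Protocol 7.1.3 says that most acute IARs with similar products occur within 2 hours of the infusion. It gives no percentage, so it points to a modest q without fixing it.

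**4. Events at stake.** Assume 9 subjects, a common Poisson rate L per subject-year, and shortening to 1 h only in those IAR-free for their first 12 months. Expected unrecorded IARs per year are at most 9 × L × e^(−L) × q(1−s). L × e^(−L) peaks at 0.368 when L = 1, which gives 3.3 × q(1−s). With q = 20% and s = 0 that is 0.66, or about 0.7 events per year across the study.

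**The case against.** The strongest reply is that IAR status depends on when the event starts, not on whether staff saw it. AEs are collected continuously, Protocol 7.3 requires specific questioning at each scheduled contact, and AE start date and time are recorded. A reaction 3 hours after infusion that is reported two weeks later still meets the ordinary 4-hour definition. This stands. It limits the loss to events that are unreported or detectable only by measurement, but does not remove it.

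It also rules out a stronger inference a reader might draw: that IAR frequency must fall by construction. With full later capture there is no fall.

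A reader might also compute that only (15×4 + 13×2 + 104×1)/(132×4) = 36% of post-infusion time is supervised, and expect recorded rates to drop by 10–40%. The documents do not support that as an expectation. Shortening is optional and needs approval, subjects with IARs may keep 4 hours, and the 36% leaves out the infusion itself, which is part of the IAR window.

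Protocol 5.1.8 does not say whether the IAR-free months run from first dose or may be any such stretch. On the first reading, shortened subjects had no earlier IARs, so their own rate cannot fall. What can be missed is newly emerging IARs. On the second, one subject's early IARs may be counted under 4 hours of observation and later ones under 1 hour.

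Finally, the over-time analysis is conditional and LAL-CL01 reported no IARs (Protocol 1.5.2), so the number of events may be small. That limits the importance of the point but does not answer it.

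**Conclusion.** The concern holds as a possible downward bias, of unknown size, in later-period IAR summaries. The mechanism is clear from the text: a fixed 4-hour window, observation that can shorten with IAR-free time on drug, and a planned evaluation over time that takes no account of this. In the grid above the recorded rate runs from no loss to 40% below the true rate. The 40% needs q = 40%, no subject still observed for 4 hours and no later capture. With half the IARs in subjects still observed for 4 hours and half the late ones captured, the shortfall is 1–10%. All of these rest on assumed p, q and s. The whole-study 4-hour count remains the right main result. The bias matters for comparisons between periods.

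**What to change.** **SAP 11.2.2.** Keep the 4-hour and any-time IAR count as the main result. For any IAR summary over time or by treatment duration, add a common-window version: onset during the infusion or within 1 hour after it ends. Show the actual observation length per infusion, by period, beside it.

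**SAP 11.4.** Show the number of readings and of subjects at each post-infusion timepoint, and note that readings beyond the shortened period come from a selected subset. Restricting late timepoints to infusions observed for 4 hours would not help. It would keep that same subset and discard valid readings from subjects observed for 2 hours.

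**Cost.** SAP wording and one derived variable. AE start times and infusion records are already collected. Observation length can be derived from the last post-infusion vital-sign time, assuming those clock times are captured. The common-window version uses fewer events and omits genuine later IARs, so it stands beside the 4-hour count and does not replace it. No change to subject monitoring is proposed.

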5.1.9 Electrocardiogram

12-lead ECGs will be obtained at the timepoints specified in Appendix A. In addition, unscheduled ECG(s) should be obtained in any subject exhibiting cardiovascular symptoms (e.g., palpitations, chest pain or tightness, tachypnea) or clinically significant changes in resting heart rate. ECGs will be reviewed by the Investigator, or designee, and any abnormalities will be specified as clinically significant (CS) or not clinically significant (NCS). If deemed to be clinically significant, these abnormalities must be recorded as Adverse Events in the electronic case report form (eCRF). In the event of any unexpected findings, subjects should be appropriately evaluated in accordance with local procedures.

- 4 weeks after starting new dose/schedule or change in lipid-lowering medication: serum lipid panel, liver panel;
- 8 weeks after starting new dose/schedule or change in lipid-lowering medication: serum lipid panel, liver panel;
- 12 weeks after starting new dose/schedule or change in lipid-lowering medication: serum lipid panel, liver panel, hematology, serum chemistry.

In the event that any of the above additional laboratory monitoring time points coincides with the standard laboratory assessment, the standard laboratory assessment will supersede the additional laboratory monitoring.

Laboratory reports will be reviewed by the Investigator, or designee, and any abnormalities will be specified as 'CS' or 'NCS'. In the event of unexplained clinically significant abnormal laboratory test results, the tests should be repeated as soon as possible (preferably within 24 hours) and followed up until they have returned to within the normal range and/or an adequate explanation has been identified.

Refer to the SOM and/or laboratory manual for further details regarding the collection, processing, and storage of these samples.

5.1.11 Exploratory Biomarkers

Blood samples for serum isolation (2 aliquots) will be obtained at the timepoints specified in the Schedule of Assessments (Appendix A) for exploratory biomarker analysis, as blood volume threshold permits. A urine sample will also be obtained at these same timepoints for exploratory biomarker analysis. These serum and urine samples will be used to identify baseline disease and dynamic markers that will help the Sponsor to better understand the pathogenesis of LAL Deficiency and related comorbidities and response to treatment. Given the rarity of LAL Deficiency and the paucity of information on disease characteristics, the definitive list of analytes remains to be determined. Samples will be stored by the Sponsor, or designee, in a secure and controlled environment until analysis.

Refer to the SOM and/or laboratory manual for further details regarding the collection, processing, and storage of these samples.

Collection of samples, for storage as described above, will be subject to discretionary approval from each center's IRB/IEC and the subject's specific written consent. This section of the protocol only applies if approval for collection of these additional samples has been granted. If the IRB/IEC does not approve the collection of additional samples, this must be stated in the approval letter.

